#### **Sexual and gender minority (SGM) sub study:**

In addition to the above, approximately n = 100 gay and bisexual patients with BPH seeking care at the Northwestern Medicine Gay and Bisexual Men's (NM-GBM) Urology Program clinic will be recruited in order to augment the representation of SGM patients. As the objective of this substudy is to evaluate the psychometric properties of the LURN SIs in an SGM population with BPH and ensure that the items reflect key concerns in this population, this sample will not receive the full battery of questionnaires listed above but will complete the simplified schedule noted in Table 2.3. These patients will be recruited through fliers distributed in-clinic that will include a link to verify eligibility and consent via REDCap. Immediately after consent, eligible participants will complete questionnaires via REDCap survey. If resources allow, questionnaires may be made available on paper. In addition, data will be extracted from the Northwestern Medicine Enterprise Data Warehouse (EDW) to obtain routinely collected objective clinical data, including urinalysis, prostate-specific antigen, uroflowmetry, post-void residual, prostate size, intravesical prostatic protrusion, cystoscopic findings, medication use and procedures received during the study period and linked to questionnaire responses using identifiers such as name, birthdate, and/or medical record number. If recruitment goals are unable to be met using this method, we will request an extract from the Northwestern EDW of patients seen at the NM-GBM in the last year that meet the study inclusion criteria for the purposes of remote recruitment. Email addresses will be obtained from the EDW for the purposes of recruitment, and eligibility and e-consent will be sent via REDCap. For eligible participants that e-consent, remote collection of the surveys listed in Table 2.3 will proceed as described above.

STU00217126  
EH22-021

Table 2.3 Study questionnaires, SGM (Schedule of assessments: baseline, and post-treatment follow-up)			
	# Items	Baseline (remote)	Week 12 (remote)
Demographics / Medical & Family History	25	X	
Treatment Plan	4	X	
Treatment Received	4		X
LURN SI-29	28	X	X
AUA-SI	8	X	X
PGI-I	1		X
SHIM	5	X	X
MSHQ-EjD	4	X	X
Ejaculatory function importance survey	3	X	
Patient Feedback Survey (optional)	6		X

**Statistical Analysis:** See statistical analysis plan.

## STUDY TIMELINES

For Aims 1 and 2, participant recruitment is expected to take 2 years, with each participant followed for 24 weeks from the latter of baseline or treatment initiation. Participants that crossover into different arms will be followed for 24 weeks within their most recent arm.

The first phase of the study is expected to last 12 months.

## PRIMARY STUDY: INCLUSION AND EXCLUSION CRITERIA

Inclusion criteria are:

- 1) Male sex
- 2) Age 50 years or older
- 3) Diagnosed by physician with BPH with planned medical or surgical treatment
- 4) Able and willing to complete questionnaires
- 5) Able and willing to provide informed consent
- 6) Ability to read, write, and speak in English
- 7) No plans to permanently move from study area in next 6 months

*Note: Only English-speaking participants will be recruited at this time because the patient-reported outcome (PRO) system to be tested is currently only available in English.*

Exclusion criteria are:

- 1) Female sex or intersex
- 2) Younger than 50 years of age
- 3) Being a prisoner or detainee
- 4) Gross hematuria
- 5) Interstitial cystitis

STU00217126  
EH22-021

- 6) Pelvic or endoscopic genitourinary surgery within the preceding 6 months (not including diagnostic cystoscopy)
- 7) History of cystitis caused by tuberculosis, radiation therapy, or Cytoxin/cyclophosphamide therapy
- 8) Ongoing symptomatic urethral stricture
- 9) Current chemotherapy or other cancer therapy
- 10) History of lower urinary tract or pelvic malignancy
- 11) Severe neurological or psychiatric disorder that would prevent study participation (e.g., bipolar disorder, psychotic disorder, Alzheimer's Disease)
- 12) Current moderate or severe substance use disorder

Deferral criteria are:

- 1) Microscopic hematuria without appropriate workup per AUA/SUFU Guidelines
- 2) Positive urine culture

### **SGM STUDY: INCLUSION AND EXCLUSION CRITERIA**

Eligibility Criteria	
Inclusion Criteria	Exclusion Criteria
Age 50 years or older	Younger than 50 years of age
Diagnosed by physician with BPH	Being a prisoner or detainee
Able and willing to complete questionnaires	Gross hematuria
Able and willing to provide informed consent	Interstitial cystitis
Ability to read, write, and speak in English	Pelvic or endoscopic genitourinary surgery within the preceding 6 months (not including diagnostic cystoscopy)
No plans to move from study area during the project period	History of cystitis caused by tuberculosis, radiation therapy, or Cytoxin/cyclophosphamide therapy
	Ongoing symptomatic urethral stricture
	Current chemotherapy, cancer therapy or pelvic malignancy
	Severe medical comorbidity that would preclude participation (e.g., Alzheimer's disease)

### **VULNERABLE POPULATIONS**

This research does not involve vulnerable populations such as neonates (of certain or uncertain viability), pregnant women, prisoners, children, or cognitively impaired adults.

STU00217126  
EH22-021

## PARTICIPANT POPULATION(S)

N/A

## RECRUITMENT METHODS

Patients—men with Benign Prostatic Hyperplasia (BPH) aged 50 years and older—will be recruited from Endeavor Health urology clinics as well as Swedish Hospital. This group has had much success in recruiting large samples of patients for research on LUTS. Both new and returning patients undergoing medical or surgical treatment for BPH will be eligible. Eligible patients will be identified in two ways: (1) A research coordinator will screen the electronic health record (EHR) for upcoming and past clinic appointments to identify patients who may be eligible. The coordinator will contact these patients by phone to describe the study and obtain informed consent remotely, which will be documented in Research Electronic Data Capture System (REDCap). Alternatively, (2) eligible patients who present for a clinic visit (either in-person or telehealth) will be referred to the coordinator to present the study, obtain informed consent (again either in-person or remotely), and document the consent and participant details in REDCap. During these interactions, research staff will explain the contents of the consent form focusing on the purpose of the study, study procedures, study duration, participants' rights and responsibilities, potential risks/benefits to participants, and how their protected health information will be used. Participants will be given the opportunity to ask questions about the study and will be provided with as much time needed to review and reach a voluntary decision on study participation.

For the 24-week duration of the study, participants will be contacted for study purposes by the research team via email, telephone, postal mail, secure end-to-end encryption, and Epic MyChart. The preferred method of communication for participants will be recorded.

For the SGM sub study, participants will be recruited from the Northwestern Medicine Gay and Bisexual Men's Urology Program at NMHC. Potential participants will be preliminarily screened by the study team and given a flier with a link to complete screening and electronic consent via a REDCap survey. In person screening and consent may be added as resources become available. Follow-up surveys approximately 12 weeks later will be administered via REDCap surveys sent by email. We will also submit our inclusion criteria to the EDW to obtain a list of patients seen at the NW-GBM clinic in the prior year for potential remote recruitment. These participants will be contacted via email addresses obtained from the EDW for remote eligibility screening and e-consent via REDCap.

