**OBJECTIVES**

STU00217126  
EH22-021

**Aim 1: Integrate routine clinical tests with PRO assessment to enhance screening, diagnosis, and management of patients with Benign Prostatic Hyperplasia (BPH).** PROs provide a cost-effective assessment strategy that can improve patient care by allowing for frequent surveillance and intervention. Men with BPH suffer from a variety of comorbid conditions (e.g., sleep disturbance, depression). We will use longitudinal modeling to identify risk factors and comorbidities that predict increased LUTS. Specifically, we will use PROs, developed by us in the LURN, to assess LUTS, including symptoms not captured by AUA-SI. We hypothesize that health variables from the PROMIS-29 Profile (e.g., sleep disturbance, depression, pain), when combined statistically with routine objective clinical variables (e.g., uroflowmetry, prostate size, intravesical prostatic protrusion) will provide unique predictive power for LUTS severity over time. Understanding these risk factors will facilitate preventative counseling and "just-in-time" interventions to improve in-clinic and telemedicine evaluations and treatment.

**Aim 2: To examine psychometric properties of the LURN SIs, including clinically meaningful differences in men with BPH receiving known effective treatment.** Longitudinal data will enable us to calculate effect sizes of the SI-10 and SI-29 from baseline to follow-up in the context of usual care, including guideline-driven treatment of BPH. LURN SIs will be anchored to patients' ratings of global change (PGI-I). A multiple-baseline design will allow estimation of test-retest reliability, while multiple longitudinal assessments provide quantitative estimates of minimally important differences (MIDs). We hypothesize that the SI-10 and SI-29 will have adequate test-retest reliability and precision to detect change across a range of severity in BPH in response to treatment.

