### **STUDY ENDPOINTS:**

Aim 1: Longitudinal trajectories of LUTS in men treated for BPH. Serial symptom data will be collected over time using the LURN SI-29 (which includes the LURN SI-10 items) and the AUA-SI. Aim 1 will identify health variables from the PROMIS-29 Profile that predict trajectories of LUTS within the individual patient.

Aim 2: Test-retest reliability and minimally important differences in the LURN SI-29 subscales and the LURN SI-10. At the end of this study, we will have established the test-retest reliability of the LURN SI questionnaires and established minimally important differences in patients with BPH after known effective treatments.

Aim 3: A care-coordination checklist for monitoring of men treated for BPH. The goal of this project is to engage men with BPH and collect their open-ended input as to what symptoms, concerns, and challenges they face over the course of their treatment with BPH. In addition, 20 clinicians

STU00217126  
EH22-021

will also be interviewed. The end product will be transcripts from up to 40 men with BPH and 20 clinicians, and an accompanying code book.

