Note: Study time points (e.g., Week 4, Week 8) are approximate – Participants will be given a time window of $\pm$ 2 weeks. The minimum time between assessments will be approximately 4 weeks. Time windows may be adjusted based on COVID-19 protocols (e.g., if a clinic visit is converted to telehealth).									

STU00217126  
EH22-021**Table 2.2 Study questionnaires, surgical/procedural intervention  
(Schedule of assessments: baseline, inter-visit follow-up, and clinic assessments)**

	# Items	Baseline (clinic)	Preop **	Week 1	Week 2	Week 4 (clinic)	Week 6	Week 8	Week 12 (clinic)	Week 24 (clinic)
LURN SI-29	28									
PROMIS-29 Profile	29									
AUA-SI	8									
Patient Global Impression of Improvement (PGI-I)	1									
National Cancer Institute Quick Food Scan	17									
3-Day Voiding Diary	9									
PROMIS-GI: Constipation	9									
PROMIS-GI: Diarrhea	6									
SHIM	5									
MSHQ-EjD	4									
STOP-BANG	8									
PRO Cognitive Function – Short Form 4a	4									
Patient Feedback Survey (optional)	6									
Note: Study time points (e.g., Week 4, Week 8) are approximate – Participants will be given a time window of $\pm$ 2 weeks. The minimum time between assessments will be approximately 4 weeks. Time windows may be adjusted based on COVID-19 protocols (e.g., if a clinic visit is converted to telehealth). ** If surgery is not immediately scheduled, complete questionnaires every 4 weeks until surgery is scheduled.										

To assess MIDs, we will administer the PGI-I as a measure of global change at each post-baseline time point. The PGI-I is a single-item questionnaire that asks respondents to rate their condition compared with prior to treatment on a 7-point scale from very much worse (1) to very much better (7). LURN SI-29 and SI-10 scores at 12 weeks post-baseline will be used to assess changes in scores since baseline.

In addition, participants will be offered the opportunity to complete a patient-response burden questionnaire (patient feedback survey) at the end of their study participation. This will provide a better understanding of how the participants perceived the PROs.

STU00217126  
EH22-021

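### Recruitment wording admits men already undergoing BPH treatment while inclusion criterion 3 requires planned treatment, so the Aim 2 effect sizes may include men whose baseline is already on treatment

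*Protocol*

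**What the plan says.** Two places in the protocol describe who may enter the primary study, and they differ on the timing of treatment.

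- **Recruitment Methods:** "Both new and returning patients undergoing medical or surgical treatment for BPH will be eligible". Coordinators are to "screen the electronic health record (EHR) for upcoming and past clinic appointments to identify patients who may be eligible".
- **Primary Study: Inclusion and Exclusion Criteria**, inclusion criterion 3: "Diagnosed by physician with BPH with planned medical or surgical treatment". Procedures Involved agrees with this, since it stratifies men by the management they are going to receive: up to 225 medical and up to 125 surgical.

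Three further places bear on timing.

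- **Study Timelines:** each man is "followed for 24 weeks from the latter of baseline or treatment initiation".
- **Exclusion criteria:** pelvic or endoscopic genitourinary surgery in the preceding 6 months is excluded. Nothing comparable is stated for current BPH medication. Data Management and Confidentiality lists current medications and the BPH treatment plan among the data to be extracted.
- **Procedures Involved:** score change for the MID work runs from baseline to 12 weeks after baseline. The global-change anchor (PGI-I) "asks respondents to rate their condition compared with prior to treatment on a 7-point scale".

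On what Aim 2 needs, Objectives says: "Longitudinal data will enable us to calculate effect sizes of the SI-10 and SI-29 from baseline to follow-up in the context of usual care". Study Endpoints promises to have "established minimally important differences in patients with BPH after known effective treatments".

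**The concern.** A change score captures a treatment's effect only if the first measurement comes before the treatment has acted. *Undergoing* describes treatment in progress; *planned* describes treatment still to come. A coordinator who follows the recruitment text could enrol a man settled on medication. His baseline would be an on-treatment score, and the following weeks would show little or none of the improvement the drug had already produced.

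Aim 2 asks whether the SI-10 and SI-29 respond to treatments known to work. Men whose improvement came before baseline add near-zero change for a reason unrelated to the questionnaires, so a responsive instrument can look less responsive than it is.

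The MIDs are exposed in a second way. For such a man the PGI-I looks back to before treatment, while his score change starts at study baseline. He may truthfully report clear improvement next to a score change near zero. The effect-size problem does not depend on this mismatch, because the effect size does not use the anchor.

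The exposure lies mainly in the medical stratum. In the surgical schedule the baseline and preoperative assessments precede the operation, and recent surgery is excluded.

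**Working it through.** **The plan's own figure.** The strata add up: 225 + 125 = 350. Against the target of at least 300 analyzable men, the allowance for unusable data is (350 − 300)/350 = 14.3%. These figures are consistent. The protocol gives none for the share of men already on treatment.

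**Can treatment precede baseline?** If treatment always began at or after baseline, the later of the two dates would always be treatment initiation, and naming baseline would add nothing. The Study Timelines clause has work to do only if treatment can come first. It does not say by how long.

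**Does another rule close the gap?** The only prior-treatment exclusion relevant to BPH management concerns surgery. Current medication is recorded, not restricted. Criterion 3 would close the gap if *planned* excludes mere continuation, but it does not say so.

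**Size, as an illustration.**

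Inputs:
- d = 0.5 in men who start treatment. This is an assumption. The value appears in the protocol only as a threshold for the SGM sub-study; no target is stated for the primary Aim 2.
- Mean change of 0 in men on stable treatment, and a within-group SD of change of 1 in both groups (assumptions).
- f = share of the medical stratum already stable, set at 10%, 25% and 50% (an assumption).
- Only the medical stratum is affected, both strata are full, and surgical men also have d = 0.5. The whole-sample share is then F = f × 225/350.

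Formulas, with x standing for f or F:
- fixed SD: (1 − x) × d
- SD of change in the mixed group: (1 − x) × d / √(1 + x(1 − x)d²)

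For example, at f = 25% in the medical stratum the fixed-SD value is 0.75 × 0.5 = 0.375. The mixed-SD value is 0.375/√(1 + 0.1875 × 0.25) = 0.375/1.023 = 0.367.

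| f | Men (of 225) | Medical, fixed SD | Medical, mixed SD | F | Whole sample, fixed SD | Whole sample, mixed SD |
|---|---|---|---|---|---|---|
| 10% | about 22 | 0.450 | 0.445 | 6.4% | 0.468 | 0.464 |
| 25% | about 56 | 0.375 | 0.367 | 16.1% | 0.420 | 0.413 |
| 50% | about 112 | 0.250 | 0.243 | 32.1% | 0.339 | 0.330 |

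The choice of SD moves the result by about 0.01 at most. The share f drives it. Limiting the calculation to men whose treatment starts after baseline returns 0.5 by construction.

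**The case against.** The strongest reply is that criterion 3 is the gate. The recruitment text says where candidates are found, and the Consent Process section has staff confirm eligibility by telephone before consent. *New and returning* may describe clinic status only: a returning man may be starting, adding or switching a drug, or moving to surgery. A past appointment may simply be the one at which treatment was planned. All of this stands as a limit on how many men are affected. It does not remove the conflict, because the recruitment sentence is itself worded as an eligibility rule.

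A reader might infer from Study Timelines that men months into steady treatment will be enrolled. The clause does not show that. A gap of days between a clinic visit and consent by telephone would fit it. So would the crossover rule, which moves men who do not complete surgery into the medical arm if they are using medical treatment.

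A reader might also infer that Aim 1 is compromised. The documents do not support this: Aim 1 asks which health variables predict symptoms over time, and treatment stage can be handled in a longitudinal model.

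Usual care and a roughly representative sample are stated intentions, so broad entry may be deliberate. That is a good reason to keep already-treated men in the cohort. It does not turn their on-treatment score into a pre-treatment baseline.

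Finally, the analysis is left to an SAP that is not at hand and that may already separate these men. If it does, the dilution is avoided, but the eligibility conflict remains in the protocol.

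**Conclusion.** The point holds in a limited form. The two eligibility statements conflict on timing, nothing in the exclusions settles it for BPH medication, and the protocol allows treatment to begin before baseline. Men already on established medication may therefore enter the medical stratum. If they are analysed with the rest, the Aim 2 effect size is pulled toward zero.

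The direction follows as long as these men change less on average than men starting treatment. The size cannot be fixed from the protocol. Under the assumptions above, the effect size in the medical stratum falls from 0.5 to between about 0.45 and 0.24 as the stable share rises from 10% to 50%. The whole-sample value falls to between about 0.47 and 0.33. The figures for the medical stratum should not be read as whole-sample losses, and none of them is a forecast.

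It would go too far to state as fact that part of the observed change will measure no treatment effect. The documents show that this can happen, not that it will.

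**What to change.** 1. Reconcile Recruitment Methods with inclusion criterion 3 so that both state the same eligibility relative to treatment start, and say whether planned treatment includes continuing an existing one.
2. If already-treated men are kept for representativeness and for Aim 1, flag them at baseline from the medication list and treatment plan that the protocol already extracts.
3. Base the Aim 2 effect sizes and MIDs on men whose treatment is started, added or changed at or after baseline. If the SAP already does this, a cross-reference in the protocol is enough.

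The cost is one reconciled sentence, one flag from data already collected, and a smaller Aim 2 responsiveness set. If the sponsor narrows entry instead of flagging, recruitment may slow and some of the intended representativeness is lost; flagging avoids both.

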## CONSENT PROCESS

Consent will follow the “Biomedical Consent Document (HRP-592)” and will always be obtained before a subject participates in any component of the current protocol. For all participants, consent will be obtained using the HRP-592 consent form. The consent form will contain a detailed description of all study procedures, as well as any possible risks and/or benefits. The participant's email will be verified before initiating any email communications upon their approval. Participants will be given an opportunity to ask any questions and contact the research team.

STU00217126  
EH22-021

Participants can be identified by PI/Co-PI referral, self-referral, or via chart review. The PI/Co-PI or study coordinator can provide a printed copy of the consent form to the patient in clinic if the patient seems to be eligible for the study. Research team members will call participants to confirm study eligibility criteria. If the participant is eligible, the research team member will answer any questions and send the consent form to the participant via REDCap, secure email, postal mail, or fax. The participant will be able to take the time to reflect on the study, discuss the study with their loved ones, and ask any additional questions that arise before providing consent. After the participant reviews the consent form in its entirety, has no further questions, and is interested in participating in the study, the consenting process will be completed by the research team. Participants may provide consent on the same day they are introduced to the study.

Participants will have the opportunity to sign the consent form in person in the clinic or via e-consent on REDCap. Screening, enrollment, and baseline can be completed on the same day or different days. The research team member will provide a printed signed copy of the consent form for patient records. If the patient signs an e-consent via REDCap, they will be able to download a copy of the signed consent at their convenience. If necessary, a copy of the signed consent form can also be mailed to the participant's home address. In the event that a consent form addendum is created, the participants will be given the opportunity to sign the addendum in clinic or via REDCap e-consent.

Shortly after the participant is consented into the study, they will receive PROs for the baseline or pre-baseline visit. PROs will be collected in accordance to the study schedule set forth for surgical or medical management, or the SGM substudy.

